12.1.4. Follow-up Period

Follow-up visits will be conducted after completion of the Treatment Period (induction and maintenance for those cohorts with maintenance treatment) or as indicated in Section 5.4. Patients who receive all 5 treatment doses or discontinue treatment for any reason except Disease Progression, or Withdrawal of consent should enter Long Term Follow up Period. These patients are to be evaluated every 9 weeks including scans until disease progression or they receive an intervening anti-cancer medication. After documented disease progression or receipt of an intervening anti-cancer medication, patients will enter Survival Follow up. During this time, patients will be contacted every 3 months for patient status (phone call or clinic visit). For subjects who discontinue treatment due to progression, follow-up should be completed approximately every 3 months as noted below (survival follow up). Completion of subsequent follow-up visits will depend on the status of the subject at the end of treatment. All subjects will be followed from the last visit until progression, initiation of a new therapy, or the duration of the study (4 years), whichever occurs first.

Following completion of the treatment and follow-up periods, all subjects will be followed for survival after completion of treatment phases and through the follow up period of the protocol. Subjects will have their survival status assessed approximately every 3 months by either a telephone, in-person contact, or chart review until study completion or termination by the Sponsor. No other data (e.g., subsequent therapies, performance status etc.) beyond survival will be collected during these calls/visits.

12.1.5. Study Participation

Each subject will have their study participation documented, including the number of cycles completed, the duration of the Follow-up Period, and if discontinuing from the study, the reason for discontinuation. At the end of each cycle, the subject continuation status for each subject will be documented on the CRF.

If for any reason, either study treatment or observations were discontinued, the reason will be recorded. The primary reasons for discontinuation will be documented:

- Adverse event(s)
- Protocol violation
- Disease progression (clinical or radiological)
- Subject withdrew consent
- Subject is lost to follow-up
- Death
- Other

Subjects who discontinue from the study should be followed until resolution and/or stabilization of any adverse event. All subjects who discontinue from the study should complete Follow-up Visits to be monitored for 28 days following the last dose of INT230-6 for the occurrence of study drug-related adverse events or other clinically significant adverse event. Subjects who are unable to complete the follow-up visits should be contacted at least once within 28 days following the last dose INT230-6.

12.1.6. Discontinuation of Subjects from Treatment

Subjects MUST discontinue investigational product (and non-investigational product at the discretion of the investigator) for any of the following reasons:

- Withdrawal of informed consent (subject's decision to withdraw for any reason)
- Any clinical adverse event (AE), laboratory abnormality or intercurrent illness which, in the opinion of the investigator, indicates that continued participation in the study is not in the best interest of the subject
- Pregnancy
- Termination of the study by Sponsor
- Loss of ability to freely provide consent through imprisonment or involuntarily incarceration
- for treatment of either a psychiatric or physical (e.g., infectious disease) illness
- Inability to comply with protocol
- Discretion of the investigator
- Disease progression or clinical deterioration as defined in Section 9.3
- Dosing delays greater than the maximum allowed dosing delays as defined in Section 8.11. All subjects who discontinue should comply with protocol specified follow-up procedures as outlined in Section 12.1.4. The only exception to this requirement is when a subject withdraws consent for all study procedures or loses the ability to consent freely (i.e., is imprisoned or involuntarily incarcerated for the treatment of either a psychiatric or physical illness).

12.1.7. Safety Evaluations

The following evaluations will be performed during the study to measure the safety and tolerability of INT230-6: clinical laboratory tests (blood and urine sampling for clinical laboratory parameters see below), pregnancy testing, ECOG performance status, physical examinations including vital sign measurements, ECG, and the incidence and severity of treatment-emergent adverse events.

Hematology

Hematology analyses will consist of the following tests:

Hemoglobin	Mean cell volume
Hematocrit	Mean cell hemoglobin
Red blood cell count	Mean cell hemoglobin concentration
Platelet count	White blood cell count (total and differential)
	Coagulation; PT, PTT/aPTT, INR

Clinical Chemistry

Clinical chemistry analyses will consist of the following tests:

Alanine aminotransferase	Creatine phosphokinase	Phosphorus
Albumin	Creatinine	Potassium
Alkaline phosphatase	Gamma-glutamyl transpeptidase	Sodium
Aspartate aminotransferase	Glucose	Thyroid Stimulating Hormone
Amylase	Lactate dehydrogenase	Total bilirubin
Bicarbonate	Lipase	Total protein
Calcium		Triglycerides
Chloride	Low density lipoprotein	Urea (or blood urea nitrogen)
Cholesterol (total)	Magnesium	Uric acid

Urinalysis

Urinalysis with microscopic analysis will be performed by the clinical laboratory. Analytes will include: pH, glucose, ketones, blood, and protein. If abnormalities are noted on any of the dipstick results, microscopic analysis will be performed.

12.2. Efficacy Evaluations

Measured qualitatively (present only at screening), absent, progression, stable, and unevaluable.

12.2.1. Primary Efficacy Parameter

The primary efficacy parameter is disease control rate (CR + PR + SD), as assessed using iRECIST (Appendix 1 Section 18.1). Per iRECIST criteria, up to 5 target tumors are identified at baseline and followed. In this study, a target tumor is a single injected tumor identified at baseline or post baseline, and up to 10 target tumors will be followed. Please refer to the Statistical Analysis Plan for tumor definitions. Subject to PI discretion, cohorts EC3, DEC2, FEC and potentially GEC may have any number of tumors injected during a given session. Record as many tumor measurements in the CRF as possible.

Evaluation of individual injected tumors will take place at every visit, with overall response (Complete, Partial, Stable, Progressive, Not Evaluable) adjudicated for each. ITR calculation could include original target tumors, bystander tumors that become injected, and new measurable lesions that are injected.

12.2.2. Additional Efficacy parameters

An additional efficacy parameter is the injected tumor response (ITR) and bystander tumor response (BTR) rate, defined as either the number of injected or non-injected bystander tumors with confirmed CR or PR, divided by the total number of injected or bystander tumors identified at baseline. Tumor response status will be assessed using iRECIST response categories for tumors that have not been injected (as detailed in Section 18.1). Up to 9 bystander tumors will be identified at baseline and followed. Evaluation of individual bystander tumors will take place at every visit, with overall response (Complete, Partial, Stable, Progressive,

Not evaluable) adjudicated for each. BTR calculation will only include bystander tumors that are not injected at that visit.

An exploratory analysis will combine all efficacy measures (injected and bystander) to calculate an overall response rate (ORR) using iRECIST criteria, with the modification to allow more than 5 target tumors in the calculation of sum of diameters. The ORR will be based on the number of subjects with confirmed CR or PR, divided by the total number of subjects with measurable disease at baseline.

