Subjects will return for safety evaluations on Days 7 and 14 for cohort B1 and weekly for all E cohorts. On Day 14 for all E cohorts, and Day 28 for cohort B1, subjects will be evaluated for additional IT injections. If the subjects have no persistent adverse events greater than Grade 2 (NCI CTCAE v 4.03) that can reasonably be attributed to the IT injection or the components of INT230-6, the subjects can receive repeat injections. Over the course of the induction phase, investigators should attempt, if safe, to dose as many tumors as possible at least 2 or 3 times at the proper dose as noted in [Table 8](#).

It is not necessary to inject each tumor on each of the 5 induction dosing sessions. For subjects who received 3 injections at the proper dose (from [Table 8](#)) in a given tumor prior to completion of 5 dosing sessions decisions regarding further treatment should be discussed with the Medical Monitor.

Note: On subsequent cycles, previously injected or new tumors may be treated. Data from animals suggest re-injecting the same tumors leads to better tumor control. The treating physician will ultimately decide which tumors will be injected, taking into consideration the response of the injected tumor(s) and the number of additional tumors that can be readily injected. Ultrasound or CT guidance may be used for needle placement to avoid injecting areas of necrosis.

Methodology:

INT230-6 will be injected into the periphery of the accessible and deep body tumors through the smallest and shortest gauge needle as possible to reach the entire depth of the tumor. For deep body tumors, ultrasonography or CT guidance at physician's choice will be used to place the needle into the tumor. The needle will be moved throughout the tumor with a pullback technique (distal, middle and proximal) if possible and be removed after each injection or when all tumors have been injected (see [Injection Manual](#) for more details).

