9.1. Additional Efficacy Analysis

Additional efficacy parameters include the duration of response (DOR), the injected tumor response (ITR), the bystander tumor response (BTR), progression free survival (PFS), and overall survival (OS). These endpoints will be summarized by treatment (see section 7 for definition of each treatment) and subgroup. Other than 1 listing reporting bystander tumors' diameter that declined over time that declined (noted below), the bystander tumor response rate (BTR) analysis will be conducted separately from the SAP from collected radiographic data.

DOR is defined as the time from first tumor assessment of CR, PR, or SD to the time of progressive disease or death due to any cause. For responders with no death or progression, DOR will be censored on the last non-PD tumor assessment or follow-up call.

The median DOR as obtained from Kaplan-Meier methods will be presented by treatment and subgroup and will include the median, 25th percentile, 75th percentile, and a 2-sided point-wise 95% confidence interval.

ITR will be based on the target tumors at the baseline visit; tumors that become target during the study will also be included in the ITR calculation at the time they are treated. The ITR is defined as the ratio of CR + PR in injected tumors / total number of injected tumors. Thus, bystander or non-target lesions dosed at later dates are not included in calculations for ITR.

The ITR will be calculated based on the maximum likelihood estimator and summarized in tables. The estimate of ITR will be accompanied by 2-sided 95% exact binomial confidence intervals as determined by the Clopper-Pearson method and assessed at each study-specified timepoint where an assessment is performed.

The BTR will follow the same definition as the ITR for bystander tumors. Note that bystander tumors that are injected on study will be included in the ITR calculation.

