4. BYSTANDER TUMOR RESPONSE RATE (BTR)

Follow the method for ITR, instead using bystander tumors. Note that if a bystander tumor is injected on study, this tumor can no longer be considered bystander after the date of injection and will be included in the ITR calculation from that injection date visit onward. This can cause the denominator to be dynamic over visits.

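### Protocol 12.2.2 and the SAP state incompatible rules for bystander tumors that are later injected, and nothing says which rule the separately run BTR analysis uses

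*Protocol*

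**What the plan says.** **Protocol 12.2.2.** BTR is part of a definition that covers injected and bystander tumors together. The numerator is "defined as either the number of injected or non-injected bystander tumors with confirmed CR or PR" and the denominator is "divided by the total number of injected or bystander tumors identified at baseline". On follow-up it says "Up to 9 bystander tumors will be identified at baseline and followed". The inclusion rule is that "BTR calculation will only include bystander tumors that are not injected at that visit". The same section also states: "Tumor response status will be assessed using iRECIST response categories for tumors that have not been injected".

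**Protocol 12.2.1.** A target tumor is an injected tumor, whether identified at baseline or later. The section sends the reader to the SAP for tumor definitions, and says that ITR could include bystanders that become injected.

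**SAP Section 9.** A bystander lesion becomes a target lesion once injected, and a target lesion never changes back.

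**SAP Appendix 1 item 4.** For BTR, "if a bystander tumor is injected on study, this tumor can no longer be considered bystander after the date of injection". The tumor then counts in ITR from the injection visit onward, and the text acknowledges that the denominator can change from visit to visit.

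**SAP 9.1.** Apart from one listing, "the bystander tumor response rate (BTR) analysis will be conducted separately from the SAP from collected radiographic data". SAP Table 2 likewise places the injected and bystander rates for the monotherapy cohorts outside the SAP.

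**SAP 13.** Changes from the protocol's statistical methods are given as none.

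**The concern.** BTR is meant to describe disease that the drug did not reach directly. The protocol synopsis treats shrinkage of non-injected tumors as a possible sign of immune activation. BTR is a secondary endpoint in the ipilimumab cohort (FEC) and exploratory in the other cohorts. It carries extra weight because SAP Section 9 says that proper RECIST or iRECIST assessment was not possible and that efficacy will rest largely on individual injected and bystander tumors.

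Two rules that classify the same tumor differently give different BTRs from the same scans. If a tumor injected with cisplatin and vinblastine shrinks and is then counted as a bystander, a local drug effect is reported as a distant one. If injected tumors are barred from the numerator but kept in the denominator, BTR is diluted instead.

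**Working it through.** The documents give no BTR figure to reproduce, so the check compares the rules and then works through illustrative cases.

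**1. The rules side by side**

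| | Protocol 12.2.2 | SAP Section 9 and Appendix 1 item 4 |
|---|---|---|
| Test for inclusion | Injection at the visit in question | Any injection so far |
| Duration of exclusion | That visit, read literally | Permanent |
| Denominator | Fixed at baseline | Changes over visits |

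**2. Does the situation arise?** Protocol 5.2.1 aims to treat as many visible tumors as possible one to three times over five induction sessions, and Protocol 5.5 says "It is not necessary to inject each tumor on each of the 5 induction dosing sessions". A baseline bystander injected once and then skipped is therefore an expected case. Under Protocol 12.1.3.1, induction doses fall on Days 0, 14, 28, 42 and 56. The first response scan is at 12 weeks ± 10 days: 12 × 7 = Day 84, range Day 74 to 94. No induction injection falls in that range. If the nine-week maintenance interval runs from Day 56 (an assumption), the first maintenance dose is due at 56 + 63 = Day 119, or Day 109 at the earliest. On the literal wording, every bystander injected during induction is thus eligible for BTR at the first scan.

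**3. One hypothetical subject.** Let b be the baseline bystanders, k those injected at an earlier session, r_i the responders among those k, and r_n the responders among the never-injected.

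- Reading A, literal per-visit rule: (r_n + r_i)/b
- Reading B, numerator limited to non-injected tumors, denominator fixed at baseline: r_n/b
- Reading C, permanent removal: r_n/(b − k)

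With b = 4, k = 2, r_i = 2, r_n = 0: A = 2/4 = 50%; B = 0/4 = 0%; C = 0/2 = 0%.

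B and C agree here only because no never-injected tumor responds. With r_n = 1: A = 3/4 = 75%; B = 1/4 = 25%; C = 1/2 = 50%. Relative to permanent removal, A is too high and B too low.

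**4. Size in general.** Let p_n be the response rate in never-injected bystanders and p_i the rate in those injected earlier. Expected BTR is:

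- A: [(b − k)p_n + k·p_i]/b, which differs from C by k(p_i − p_n)/b
- B: (b − k)p_n/b, which differs from C by −k·p_n/b
- C: p_n

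The rates below are assumed, since the documents give none. b = 9 is the protocol's maximum number of followed bystanders.

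| p_n, p_i | k | A | B | C |
|---|---|---|---|---|
| 5%, 30% | 1 | 7.8% | 4.4% | 5% |
| 5%, 30% | 3 | 13.3% | 3.3% | 5% |
| 5%, 30% | 5 | 18.9% | 2.2% | 5% |
| 10%, 30% | 1 | 12.2% | 8.9% | 10% |
| 10%, 30% | 3 | 16.7% | 6.7% | 10% |
| 10%, 30% | 5 | 21.1% | 4.4% | 10% |
| 10%, 50% | 1 | 14.4% | 8.9% | 10% |
| 10%, 50% | 3 | 23.3% | 6.7% | 10% |
| 10%, 50% | 5 | 32.2% | 4.4% | 10% |

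Example, 10% and 30% with k = 3: A = (6 × 0.10 + 3 × 0.30)/9 = 1.5/9 = 16.7%; B = 0.6/9 = 6.7%.

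**5. Where does the tumor go instead?** SAP 9.1 says in one sentence that bystanders dosed later are not part of ITR, and in another that bystanders injected on study are. Protocol 12.2.1 says only that ITR could include them. The plan therefore does not settle in which rate a later-injected bystander belongs.

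**The case against.** The strongest reply is that the documents, read together, already exclude injected tumors from BTR. Protocol 12.2.2 itself limits the numerator to non-injected bystanders and ties the response categories to tumors that have not been injected. Protocol 12.2.1 makes an injected tumor a target and defers to the SAP for tumor definitions. SAP Section 9 then makes that change permanent. On this reading, a tumor injected at dose 3 is no longer a bystander at week 12, so the per-visit sentence cannot bring it back. The SAP listing of abscopal effects follows the same logic, counting only shrinkage before injection. Running BTR separately does not revoke the SAP's tumor classes, and the entry of none in SAP 13 may only mean that the sponsor saw no conflict.

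Most of this stands. Permanent removal is probably what was intended, and the literal sentence is one reading among several. It does not close the matter:

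- The deferral concerns tumor definitions, whereas the sentence in question is a calculation rule.
- The denominators conflict whichever tumor definition applies.
- The analysis that will produce BTR is placed outside the document holding the better rule, and nothing ties the two together.
- SAP 9.1 is inconsistent on ITR for the same tumors.

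A reader might go further and infer that, with BTR run outside the SAP, the protocol rule governs and direct drug effect will be reported as bystander response. The documents do not support that. The specification of the separate analysis is not in them, and the protocol text itself leads back to the SAP for tumor definitions.

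**Conclusion.** There is a real and undeclared conflict between the protocol and the SAP over BTR. It is not a demonstrated inflation of BTR. The hypothetical subject yields 2/4, 0/4 or 0/2 from identical data. Under the assumed rates with nine bystanders, the literal rule adds about 2 to 22 percentage points (12.2% against 10% at the low end, 32.2% against 10% at the high end). Limiting only the numerator removes about 0.6 to 5.6 points (4.4% against 5%, and 4.4% against 10%).

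These sizes rest on response rates and numbers of later-injected tumors that the documents do not give. They also assume that tumors chosen for later injection would otherwise respond like the remaining bystanders. The upward direction of the literal rule needs only that injected tumors respond more often than non-injected ones.

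The consequence is confined to BTR, and to ITR through the inconsistent sentences in SAP 9.1. The primary safety endpoint and the disease control rate do not depend on it. It should be corrected because BTR is secondary in FEC and bears on any claim of a systemic immune effect.

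**What to change.** 1. In Protocol 12.2.2, replace the per-visit sentence with the rule of SAP Appendix 1 item 4: from its first injection, a tumor leaves both the numerator and the denominator of BTR for all later assessments.
2. Define the denominator at each assessment as the baseline bystander tumors not injected at or before that date.
3. State in SAP 9.1, and in the specification of the separate BTR analysis, that this rule applies.
4. List the difference from the protocol in SAP 13.
5. Reconcile the two ITR sentences in SAP 9.1, so that a later-injected bystander is assigned to one rate only.

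The cost is a few sentences. No new data should be needed, because Appendix 1 item 4 already presupposes the injection date of each tumor. The downside is a smaller BTR denominator, hence less precision, and possibly a less favourable BTR.

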12.2.3. Exploratory Biomarkers of Immune Response

Additional sample collections efficacy may be performed to measure the impact of INT230-6 upon the potency of the immune response and evaluate biomarkers that may ultimately be associated with beneficial clinical responses (refer to [PK and Biomarker Manual](#) for additional information on biopsies).

Samples (including serum and PBMCs) for evaluation of cytokines, lymphocyte phenotype (by flow cytometry), quantitative immunoglobulins, disease-related biomarkers (or antibody responses to selected antigens), cellular immune responses to tumor antigens, and a panel of recall non-tumor antigens may be assessed.

Available slides and tissue samples from tumor biopsies collected before enrollment in this study may also be examined for tumor markers and inflammatory infiltrates.

Readily accessible tissue from the research-related biopsies will be collected at baseline and then on study (refer to [PK and Biomarker Manual](#) for additional information). Tissue samples from these tumor biopsies, as well as from any other clinically indicated and consented biopsies conducted during the study will be collected, to assess morphology and the presence or absence of inflammatory infiltrates, and their cellular characterization.

Additional sample collections and analyses may be performed at selected study sites with a site-specific amendment. All samples collected for these exploratory analyses will be stored and may be used for subsequent research relevant to tumor immune response.

Blood biomarkers collections have been eliminated in Amendment 6.

The following table is a summary of the samples to be collected.

Table 14: Tumor Biopsy and Genetic Sample collection

Blood biomarkers collections have been eliminated in Amendment 6.

Collection timing	Tumor Biopsy	Whole Blood Gene Expression	Whole Blood SNP
Screening		X	X
Cycle 1, Day 0 (prior to treatment)	X ¹		
Cycle 2, Day 0 (prior to treatment)	X ¹		

¹Following the completion of 20 subjects through at least 3 treatment cycles each with a minimum of 10 subjects having had deep tumors injections and review by the SSC of the safety, a biopsy may to be taken immediately prior to injection of INT230-6 (refer to [PK and Biomarker Manual](#) for additional information). Safety of biopsying to be reviewed after 5 subjects by SSC. As of this amendment, safety has been demonstrated, and all subjects will have tumor biopsies.

